## **5.5 Rescue Medications & Supportive Care**

### **5.5.1 Supportive Care Guidelines**

Subjects should receive appropriate supportive care measures as deemed necessary by the treating investigator. Suggested supportive care measures for the management of adverse

events with potential immunologic etiology are outlined below. Where appropriate, these guidelines include the use of oral or intravenous treatment with corticosteroids as well as additional anti-inflammatory agents if symptoms do not improve with administration of corticosteroids. Note that several courses of steroid tapering may be necessary as symptoms may worsen when the steroid dose is decreased. For each disorder, attempts should be made to rule out other causes such as metastatic disease or bacterial or viral infection, which might require additional supportive care. The treatment guidelines are intended to be applied when the investigator determines the events to be related to pembrolizumab.

Note: if after the evaluation the event is determined not to be related, the investigator does not need to follow the treatment guidance (as outlined below). Refer to Section 5.2.1 for dose modification.

It may be necessary to perform conditional procedures such as bronchoscopy, endoscopy, or skin photography as part of evaluation of the event.

- **Pneumonitis:**

- For **Grade 2 events**, treat with systemic corticosteroids. When symptoms improve to Grade 1 or less, steroid taper should be started and continued over no less than 4 weeks.
- For **Grade 3-4 events**, immediately treat with intravenous steroids. Administer additional anti-inflammatory measures, as needed.
- Add prophylactic antibiotics for opportunistic infections in the case of prolonged steroid administration.

- **Diarrhea/Colitis:**

Subjects should be carefully monitored for signs and symptoms of enterocolitis (such as diarrhea, abdominal pain, blood or mucus in stool, with or without fever) and of bowel perforation (such as peritoneal signs and ileus).

- All subjects who experience diarrhea/colitis should be advised to drink liberal quantities of clear fluids. If sufficient oral fluid intake is not feasible, fluid and electrolytes should be substituted via IV infusion. For Grade 2 or higher diarrhea, consider GI consultation and endoscopy to confirm or rule out colitis.
  - For **Grade 2 diarrhea/colitis**, administer oral corticosteroids.
  - For **Grade 3 or 4 diarrhea/colitis**, treat with intravenous steroids followed by high dose oral steroids.
  - When symptoms improve to Grade 1 or less, steroid taper should be started and continued over no less than 4 weeks.
- **Type 1 diabetes mellitus (if new onset, including diabetic ketoacidosis [DKA]) or  $\geq$  Grade 3 Hyperglycemia, if associated with ketosis (ketonuria) or metabolic acidosis (DKA)**

- For **T1DM** or **Grade 3-4** Hyperglycemia
  - Insulin replacement therapy is recommended for Type I diabetes mellitus and for Grade 3-4 hyperglycemia associated with metabolic acidosis or ketonuria.
  - Evaluate patients with serum glucose and a metabolic panel, urine ketones, glycosylated hemoglobin, and C-peptide.
- **Hypophysitis:**
  - For **Grade 2** events, treat with corticosteroids. When symptoms improve to Grade 1 or less, steroid taper should be started and continued over no less than 4 weeks. Replacement of appropriate hormones may be required as the steroid dose is tapered.
  - For **Grade 3-4** events, treat with an initial dose of IV corticosteroids followed by oral corticosteroids. When symptoms improve to Grade 1 or less, steroid taper should be started and continued over no less than 4 weeks. Replacement of appropriate hormones may be required as the steroid dose is tapered.
- **Hyperthyroidism or Hypothyroidism:**

Thyroid disorders can occur at any time during treatment. Monitor patients for changes in thyroid function (at the start of treatment, periodically during treatment, and as indicated based on clinical evaluation) and for clinical signs and symptoms of thyroid disorders.

  - **Grade 2** hyperthyroidism events (and **Grade 2-4** hypothyroidism):
    - In hyperthyroidism, non-selective beta-blockers (e.g. propranolol) are suggested as initial therapy.
    - In hypothyroidism, thyroid hormone replacement therapy, with levothyroxine or liothyronine, is indicated per standard of care.
  - **Grade 3-4** hyperthyroidism
    - Treat with an initial dose of IV corticosteroid followed by oral corticosteroids. When symptoms improve to Grade 1 or less, steroid taper should be started and continued over no less than 4 weeks. Replacement of appropriate hormones may be required as the steroid dose is tapered.
- **Hepatic:**
  - For **Grade 2** events, monitor liver function tests more frequently until returned to baseline values (consider weekly).
    - Treat with IV or oral corticosteroids
  - For **Grade 3-4** events, treat with intravenous corticosteroids for 24 to 48 hours.

- When symptoms improve to Grade 1 or less, a steroid taper should be started and continued over no less than 4 weeks.
- **Renal Failure or Nephritis:**
  - For **Grade 2** events, treat with corticosteroids.
  - For **Grade 3-4** events, treat with systemic corticosteroids.
  - When symptoms improve to Grade 1 or less, steroid taper should be started and continued over no less than 4 weeks.
- **Management of Infusion Reactions:** Signs and symptoms usually develop during or shortly after drug infusion and generally resolve completely within 24 hours of completion of infusion.

Table 3 Infusion Reaction Treatment Guidelines

NCI CTCAE Grade	Treatment	Premedication at subsequent dosing
Grade 1 Mild reaction; infusion interruption not indicated; intervention not indicated	Increase monitoring of vital signs as medically indicated until the subject is deemed medically stable in the opinion of the investigator.	None
Grade 2 Requires infusion interruption but responds promptly to symptomatic treatment (e.g., antihistamines, NSAIDS, narcotics, IV fluids); prophylactic medications indicated for < =24 hrs	Stop Infusion and monitor symptoms. Additional appropriate medical therapy may include but is not limited to: IV fluids Antihistamines NSAIDS Acetaminophen Narcotics Increase monitoring of vital signs as medically indicated until the subject is deemed medically stable in the opinion of the investigator. If symptoms resolve within one hour of stopping drug infusion, the infusion may be restarted at 50% of the original infusion rate (e.g., from 100 mL/hr to 50 mL/hr). Otherwise dosing will be held until symptoms resolve and the subject should be premedicated for the next scheduled dose. Subjects who develop Grade 2 toxicity despite adequate premedication should be permanently discontinued from further trial treatment administration.	Subject may be premedicated 1.5h (± 30 minutes) prior to infusion of pembrolizumab (MK-3475) with:  Diphenhydramine 50 mg po (or equivalent dose of antihistamine).  Acetaminophen 500-1000 mg po (or equivalent dose of antipyretic).
Grades 3 or 4  Grade 3: Prolonged (i.e., not rapidly responsive to symptomatic medication and/or brief interruption of infusion); recurrence of symptoms following initial improvement; hospitalization indicated for other clinical sequelae (e.g., renal impairment, pulmonary infiltrates)  Grade 4:	Stop Infusion. Additional appropriate medical therapy may include but is not limited to: IV fluids Antihistamines NSAIDS Acetaminophen Narcotics Oxygen Pressors Corticosteroids Epinephrine	No subsequent dosing

NCI CTCAE Grade	Treatment	Premedication at subsequent dosing
Life-threatening; pressor or ventilatory support indicated	Increase monitoring of vital signs as medically indicated until the subject is deemed medically stable in the opinion of the investigator. Hospitalization may be indicated. Subject is permanently discontinued from further trial treatment administration.	
Appropriate resuscitation equipment should be available in the room and a physician readily available during the period of drug administration.		

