#### **5.3.1 Pembrolizumab**

Adverse events (both non-serious and serious) associated with pembrolizumab exposure may represent an immunologic etiology. These adverse events may occur shortly after the first dose or several months after the last dose of treatment. Pembrolizumab must be withheld for drug-related toxicities and severe or life-threatening AEs as per 3 below. See Section 5.6 for supportive care guidelines, including use of corticosteroids.

Toxicities unrelated to pembrolizumab will not ordinarily result in the modification of pembrolizumab dose. AEs will be defined based on the National Cancer Institute (NCI) Common Terminology Criteria for Adverse Events (CTCAE) version 4.

Table 3 Dose Modification Guidelines for Drug-Related Adverse Events

General instructions:				

 
1. Corticosteroid taper should be initiated upon AE improving to Grade 1 or less and continue to taper over at least 4 weeks.
 
2. For situations where pembrolizumab has been withheld, pembrolizumab can be resumed after AE has been reduced to Grade 1 or 0 and corticosteroid has been tapered. Pembrolizumab should be permanently discontinued if AE does not resolve within 12 weeks of last dose or corticosteroids cannot be reduced to <math>\leq 10</math> mg prednisone or equivalent per day within 12 weeks.
 
3. For severe and life-threatening irAEs, IV corticosteroid should be initiated first followed by oral steroid. Other immunosuppressive treatment should be initiated if irAEs cannot be controlled by corticosteroids.
 
				
Immune-related AEs	Toxicity grade or conditions (CTCAEv4.0)	Action taken to pembrolizumab	irAE management with corticosteroid and/or other therapies	Monitor and follow-up
Pneumonitis	Grade 2	Withhold	
 
• Administer corticosteroids (initial dose of 1-2 mg/kg prednisone or equivalent) followed by taper
 
	
 
• Monitor participants for signs and symptoms of pneumonitis
 
• Evaluate participants with suspected pneumonitis with radiographic imaging and initiate corticosteroid treatment
 
• Add prophylactic antibiotics for opportunistic infections
 

	Grade 3 or 4, or recurrent Grade 2	Permanently discontinue		

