Hyperthyroidism	Grade 2	Continue	
 
Treat with non-selective beta-blockers (eg, propranolol) or thionamides as appropriate
 
	
 
Monitor for signs and symptoms of thyroid disorders.
 

	Grade 3 or 4	Withhold or permanently discontinue 		
Hypothyroidism	Grade 2-4	Continue	
 
Initiate thyroid replacement hormones (eg, levothyroxine or liothyronine) per standard of care
 
	
 
Monitor for signs and symptoms of thyroid disorders.
 

Nephritis and Renal dysfunction	Grade 2	Withhold	
 
Administer corticosteroids (prednisone 1-2 mg/kg or equivalent) followed by taper.
 
	
 
Monitor changes of renal function
 

	Grade 3 or 4	Permanently discontinue		
Myocarditis	Grade 1 or 2	Withhold	
 
Based on severity of AE administer corticosteroids
 
	
 
Ensure adequate evaluation to confirm etiology and/or exclude other causes
 

	Grade 3 or 4	Permanently discontinue		
All other immune-related AEs	Intolerable/ persistent Grade 2	Withhold	

Based on type and severity of AE administer corticosteroids

	

Ensure adequate evaluation to confirm etiology and/or exclude other causes

	Grade 3	Withhold or discontinue based on the type of event. Events that require discontinuation include and not limited to: Guillain-Barre Syndrome, encephalitis		
	Grade 4 or recurrent Grade 3	Permanently discontinue		
1. Withhold or permanently discontinue pembrolizumab is at the discretion of the investigator or treating physician. NOTE: For participants with Grade 3 or 4 immune-related endocrinopathy where withhold of pembrolizumab is required, pembrolizumab may be resumed when AE resolves to $\leq$ Grade 2 and is controlled with hormonal replacement therapy or achieved metabolic control (in case of T1DM).				

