#### **7 Calendar-Day Telephone or Fax Report**

The Sponsor-Investigator is required to notify the FDA of a fatal or life-threatening adverse event that is unexpected and assessed by the investigator to be possibly related to the use of *investigational agents*. An unexpected adverse event is one that is not already described in the most recent Guidance for Investigator section of the Investigator's Brochure. Such reports are

to be telephoned or faxed to the FDA, Merck and Exelixis within 7 calendar days of the first learning of the event.

15 Calendar-Day Written Report

The Sponsor-Investigator is also required to notify the FDA and all participating investigators, in a written IND Safety Report, of any serious unexpected adverse event that is considered reasonably or possibly related to the use of investigational agent.

Written IND Safety Reports with analysis of similar events are to be submitted to the FDA, Exelixis, and Merck within 15 calendar days of first learning of the event. The FDA prefers these reports on a MedWatch 3500 Form but alternative formats (eg, summary letter) are acceptable.

FDA Fax number of IND Safety Reports: [name]

All written IND Safety Reports submitted to the FDA by the Sponsor-Investigator must also be faxed to:

Exelixis Drug Safety  
[contact]

Merck Global Safety  
[contact]

Table 6 Evaluating Adverse Events

An investigator who is a qualified physician, will evaluate all adverse events as to:

V4.0 CTCAE Grading	Grade 1	Mild; asymptomatic or mild symptoms; clinical or diagnostic observations only; intervention not indicated.
	Grade 2	Moderate; minimal, local or noninvasive intervention indicated; limiting age-appropriate instrumental ADL.
	Grade 3	Severe or medically significant but not immediately life-threatening; hospitalization or prolongation of hospitalization indicated; disabling; limiting self-care ADL.
	Grade 4	Life threatening consequences; urgent intervention indicated.
	Grade 5	Death related to AE
Seriousness	A serious adverse event is any adverse event occurring at any dose or during any use of investigational product that:	
	†Results in death; or	
	†Is life threatening; or places the subject, in the view of the investigator, at immediate risk of death from the event as it occurred (Note: This does not include an adverse event that, had it occurred in a more severe form, might have caused death.); or	

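### Grade 3-4 hyperthyroidism: the Table 3 row, Table 3's general instructions and Section 5.5.1 do not yield one treatment instruction or one condition for restarting pembrolizumab

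*Combined protocol and SAP*

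**What the plan says.** Table 3 here means the dose-modification table in Section 5.3.1; the infusion-reaction table in 5.5.1 carries the same number.

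- **Table 3, hyperthyroidism row.** The management text is "Treat with non-selective beta-blockers (eg, propranolol) or thionamides as appropriate", printed on the Grade 2 line. The Grade 3 or 4 line gives the action on pembrolizumab, "Withhold or permanently discontinue", left to the physician's discretion by footnote 1. No separate treatment text is printed on that line.
- **Table 3, general instruction 3.** "For severe and life-threatening irAEs, IV corticosteroid should be initiated first followed by oral steroid". No exception for thyroid events is stated.
- **Table 3, general instruction 1.** "Corticosteroid taper should be initiated upon AE improving to Grade 1 or less and continue to taper over at least 4 weeks".
- **Section 5.5.1, Grade 3-4 hyperthyroidism.** "Treat with an initial dose of IV corticosteroid followed by oral corticosteroids", with a taper of at least 4 weeks once symptoms reach Grade 1 or less. Beta-blockers appear under Grade 2 only, and thionamides are not mentioned.
- **Restart, Table 3 general instruction 2.** "pembrolizumab can be resumed after AE has been reduced to Grade 1 or 0 and corticosteroid has been tapered".
- **Restart, Table 3 endocrinopathy note.** After a Grade 3 or 4 endocrinopathy, "pembrolizumab may be resumed when AE resolves to" Grade 2 or less and is controlled by hormone replacement or, in type 1 diabetes, by metabolic control.

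**The concern.** A site that opens the hyperthyroidism row finds no steroid. A site that opens 5.5.1, or applies the general instructions at the head of Table 3, finds IV then oral steroid with a taper of at least 4 weeks. The two Table 3 conditions for restarting pembrolizumab also set different grades. For an individual patient, the stake is whether systemic steroid is given and when pembrolizumab resumes. For the trial, the stake is that similar events could be handled differently, with nothing in the protocol to show which handling was intended.

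**Working it through.** No sample size, error rate or event count enters this point, so the check compares texts.

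**1. Does the row's treatment cell reach Grade 3-4?** The table text does not show where the cell ends. The layout favours a cell spanning both lines. The AST/ALT row prints a second management entry where treatment differs by grade. The pneumonitis, colitis, hypophysitis and nephritis rows print one entry only. If that entry belonged to the lower grade alone, their higher grades would have no treatment listed. Against this, 5.5.1 puts beta-blockers under Grade 2 only.

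**2. What follows under each reading?**

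| Reading of the cell | Row, Grade 3-4 | General instructions 1 and 3 | Section 5.5.1 | Result |
|---|---|---|---|---|
| Spans both grades | Beta-blockers or thionamides | IV then oral steroid, taper | IV then oral steroid, taper | Row differs from both other texts |
| Grade 2 only | No treatment listed | IV then oral steroid, taper | IV then oral steroid, taper | Treatment texts agree |

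**3. Does general instruction 3 settle it?** Table 6 in Section 7.3 describes Grade 3 as "Severe or medically significant but not immediately life-threatening" and Grade 4 as life threatening, so read literally the instruction covers Grade 3-4 hyperthyroidism. But the table's other endocrine rows do not follow it uniformly. Hypothyroidism at Grades 2-4 is managed with thyroid hormone while pembrolizumab continues. New type 1 diabetes, or Grade 3-4 hyperglycemia with beta-cell failure, is managed with insulin or anti-hyperglycemics. Section 5.5.1 names no steroid for either. A reader therefore cannot tell whether instruction 3 adds to the hyperthyroidism row, replaces it, or gives way to it.

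**4. Restart.** Take a patient whose event has come down to Grade 2 and who meets the note's control condition.

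- Endocrinopathy note: pembrolizumab may resume.
- General instruction 2: it may not, because Grade 0-1 and a tapered steroid are needed.
- General instruction 1 and 5.5.1: a patient on steroid would not yet have started the taper, which begins only at Grade 1 or less.

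This difference lies within Table 3 and remains under either reading in step 2.

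**5. Is there a rule of precedence?** The introduction to Table 3 sends the reader to Section 5.6 for supportive care, but 5.6 covers diet, contraception, pregnancy and nursing. Section 5.5.1 sends the reader to 5.2.1 for dose modification, but 5.2.1 lists the XL888 dose levels. Neither reference reaches its target, and no statement says which text governs.

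**The case against.** The strongest reply is that Table 3 already contains the steroid route. General instructions 1 and 3 give the same sequence and taper as 5.5.1, and if the row's cell belongs to Grade 2 only, the treatment texts agree. That is correct as far as it goes, and it rules out saying that Table 3 as a whole omits steroids. It does not close the point, because the table's layout favours the spanning cell and the other endocrine rows show that instruction 3 is not applied uniformly.

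Second, 5.5.1 offers its measures as suggestions, as the treating investigator deems necessary, and intends them for events judged related to pembrolizumab. That also stands: 5.5.1 does not mandate steroid. Suggested guidance that differs from the table beside it still leaves the site without a clear instruction.

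Third, the endocrinopathy note can be read as a specific exception to general instruction 2. Instruction 2 may not require a finished taper either, since its discontinuation clause uses a threshold of 10 mg prednisone or less per day. Both readings are reasonable. The protocol states neither, and the note does not say how it applies to a patient on steroid.

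Fourth, the ambiguity does not alter the dose-limiting toxicity definition. Section 5.2.3 classifies such an event by grade, relatedness and timing, not by how it is treated. That stands.

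**Conclusion.** The point holds as an inconsistency in wording with consequences for the individual patient. The treatment conflict rests on the assumption that the row's cell spans both grade lines, which is likely but unconfirmed. The unclear restart condition and the two misdirected cross-references do not depend on that assumption. The documents give no expected rate of Grade 3-4 hyperthyroidism among the 38 to 50 planned patients, so the effect on trial results cannot be sized and may be small.

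A reader might infer more than the documents support:

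- **That every such event would be handled in two different ways.** The general instructions and 5.5.1 agree with each other, and the row's reach is unconfirmed.
- **That a fixed number of pembrolizumab doses would be missed.** Pembrolizumab is withheld or discontinued at Grade 3-4 under either treatment. If restart had to await a completed taper, the hold would be the time to reach Grade 1 or less plus at least 4 × 7 = 28 days. The first term is not given, so no upper limit on missed 21-day doses follows.
- **That the steroid text was carried over from hypophysitis by mistake.** The wording is similar, but that does not show which text is in error.
- **That the immune read-outs would be suppressed.** The documents do not say so. Moreover, blood sampling covers the first 9 weeks and end of treatment, and the repeat biopsy falls in week 3 of cycle 1, so only events before those samples could matter.

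**What to change.** Reconcile the Table 3 hyperthyroidism row, general instructions 1 to 3, the endocrinopathy note and Section 5.5.1, so that Grade 3-4 hyperthyroidism has one treatment instruction and one condition for restarting pembrolizumab. Make the grade coverage of the row's management cell explicit, and say whether general instruction 3 applies to the endocrine rows. Correct the reference to Section 5.6 in the introduction to Table 3 and the reference to Section 5.2.1 in 5.5.1. State which text governs if the two differ. The choice of treatment and of restart condition belongs to the sponsor's clinicians. The cost is wording only; no procedure, visit or patient is added.

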## 5.6 Diet/Activity/Other Considerations

### 5.6.1 Diet

Subjects should maintain a normal diet unless modifications are required to manage an AE such as diarrhea, nausea or vomiting. Seville orange, star fruit, grapefruit and their juices affect P450 and PgP activity and concomitant use with XL888 should be avoided.

### 5.6.2 Contraception

Pembrolizumab and XL888 may have adverse effects on a fetus in utero. Furthermore, it is not known if pembrolizumab and XL888 have transient adverse effects on the composition of sperm.

For this trial, male subjects will be considered to be of non-reproductive potential if they have azoospermia (whether due to having had a vasectomy or due to an underlying medical condition).

Female subjects will be considered of non-reproductive potential if they are either:

- (1) postmenopausal (defined as at least 12 months with no menses without an alternative medical cause; in women < 45 years of age a high follicle stimulating hormone (FSH) level in the postmenopausal range may be used to confirm a post-menopausal state in women not using hormonal contraception or hormonal replacement therapy. In the absence of 12 months of amenorrhea, a single FSH measurement is insufficient.);

OR

- (2) have had a hysterectomy and/or bilateral oophorectomy, bilateral salpingectomy or bilateral tubal ligation/occlusion, at least 6 weeks prior to screening;

OR

- (3) has a congenital or acquired condition that prevents childbearing.

Female and male subjects of reproductive potential must agree to avoid becoming pregnant or impregnating a partner, respectively, while receiving study drug and for 120 days after the last dose of study drug by complying with one of the following:

(1) practice abstinence† from heterosexual activity;

OR

(2) use (or have their partner use) acceptable contraception during heterosexual activity.

Acceptable methods of contraception are‡:

Single method (one of the following is acceptable):

- intrauterine device (IUD)
- vasectomy of a female subject's male partner
- contraceptive rod implanted into the skin

Combination method (requires use of two of the following):

- diaphragm with spermicide (cannot be used in conjunction with cervical cap/spermicide)
- cervical cap with spermicide (nulliparous women only)
- contraceptive sponge (nulliparous women only)
- male condom or female condom (cannot be used together)
- hormonal contraceptive: oral contraceptive pill (estrogen/progestin pill or progestin-only pill), contraceptive skin patch, vaginal contraceptive ring, or subcutaneous contraceptive injection

†Abstinence (relative to heterosexual activity) can be used as the sole method of contraception if it is consistently employed as the subject's preferred and usual lifestyle and if considered acceptable by local regulatory agencies and ERCs/IRBs. Periodic abstinence (e.g., calendar, ovulation, sympto-thermal, post-ovulation methods, etc.) and withdrawal are not acceptable methods of contraception.

‡If a contraceptive method listed above is restricted by local regulations/guidelines, then it does not qualify as an acceptable method of contraception for subjects participating at sites in this country/region.

Subjects should be informed that taking the study medication may involve unknown risks to the fetus (unborn baby) if pregnancy were to occur during the study. In order to participate in the study subjects of childbearing potential must adhere to the contraception requirement (described above) from the day of study medication initiation (or 14 days prior to the initiation

of study medication for oral contraception) throughout the study period up to 120 days after the last dose of trial therapy. If there is any question that a subject of childbearing potential will not reliably comply with the requirements for contraception, that subject should not be entered into the study.

